Visit week 0 (site visit): The study patient will have a physical exam and a urine pregnancy test. If subject is a woman of child-bearing potential, a reliably and highly effective contraceptive method will be confirmed. The patient's AE and symptom diary will be reviewed and the clinically modified PDAI calculated. The patient's concomitant medications will be reviewed. If the study patient fulfils all inclusion criteria and does not have an exclusion criterion the study patient will be randomized to either the placebo or the liraglutide group and a unique study ID number will be assigned, which will appear on all medication packs, which will be containing treatment until week 6 period 1. A glucometer, supplies, and instructions for use will be provided as well as a review of signs and symptoms of hypoglycemia, plus a review of hypoglycemic protocol and reporting form.

Visits week 1 and 2 (phone visits): The coordinator will ask the study patient if adverse events occurred and will review the adverse event diary with the study patient. The coordinator will also evaluate the web registered clinical components of the mPDAI of the last 3 days before the phone call (stool frequency, rectal bleeding, fecal urgency/ abdominal cramping, fever) as well as the concomitant medications. At visit week 1 and 2 the patient will be asked to collect/send in a stool sample for the next (in person or as mail in collected days -2 - +2 around the visit date). There will also be a review of glucose diary and hypoglycemic protocol and reporting form. If subject is a woman of child-bearing potential, a reliably and highly effective contraceptive method will be confirmed.

Visit week 4 (site visit): The coordinator will review the adverse events, which occurred since the previous visit. A physical exam and blood tests will be performed and the mPDAI will be calculated. The concomitant medications will be assessed. If subject is a woman of child-bearing potential, a reliably and highly effective contraceptive method will be confirmed. A stool sample will be collected from the patient either at visit or days -2 - +2 around the study visit or as mail in. Instructions to either mail in or provide in person stool sample at visit week 6 period 1. In case of early crossover female patients will provide urine samples for pregnancy test at week 4. There will also be a review of glucose diary and hypoglycemic protocol and reporting form.

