If at visit week 4 the bowel frequency of the patient did not respond to treatment (at least a 15% decrease compared to baseline the patient can proceed to early crossover. The patient will be given study drug (either the placebo or the liraglutide group) in medication packs with his unique study ID medication packs, which will be containing treatment until week 12 and be instructed to bring back the study medication from study period 1 at the final visit of period 2 (week 12). He will be instructed to start injections on day 6 after 5 days of washout. The day he starts will be defined as week 6 period 2.

Visit week 6 period 1 (site visit): If the patient did not qualify for early crossover, he will come to visit week 6 period 1 the coordinator will review the adverse events, which occurred since the previous visit. A physical exam and blood tests will be performed and the mPDAI will be calculated. The concomitant medications will be assessed. If subject is a woman of child-bearing potential, a reliably and highly effective contraceptive method will be confirmed. A stool sample will be collected from the patient either at visit or days -2 - +2 around the study visit as mail in. Female patients will provide urine samples for pregnancy test at week 6 period 1. The patient will be given either the placebo or the liraglutide group with his unique study ID for period 2 and will be instructed to start injections on day 6 after 5 days of washout. The day he starts will be defined as week 6 period 2. The patients will be also be instructed to bring back the study medication from study period 1 at the final visit of period 2 (week 12). There will also be a review of glucose diary and hypoglycemic protocol and reporting form.

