Visits week 7 and 8 (phone visits): The coordinator will ask the study patient if adverse events occurred and will review the adverse event diary with the study patient. The coordinator will also evaluate the web registered clinical components of the mPDAI of the last 3 days before the phone call (stool frequency, rectal bleeding, fecal urgency/ abdominal cramping, fever) as well as the concomitant medications. At visit week 7 and 8 the patient will be asked to send in a stool sample for visit week the next visit (in person or as mail in collected days -2 - +2 around the visit date). There will also be a review of glucose diary and hypoglycemic protocol and reporting form. If subject is a woman of child-bearing potential, a reliably and highly effective contraceptive method will be confirmed.

Visit week 10 (site visit): The coordinator will review the adverse events, which occurred since the previous visit. A physical exam and blood tests will be performed and the mPDAI will be

calculated. The concomitant medications will be assessed. If subject is a woman of child-bearing potential, a reliable and highly effective contraceptive method will be confirmed and they will provide urine samples for pregnancy test at week 10. A stool sample will be collected from the patient either at visit or days -2 - +2 around the study visit or as mail in. Instructions to either mail in or provide in person stool sample at visit week 12. There will also be a review of glucose diary and hypoglycemic protocol and reporting form.

If at visit week 10 the bowel frequency of the patient did not respond to treatment (at least a 15% decrease compared to baseline this visit will be classified as end of treatment (week 12). If the patient meets the criteria of non-response, he/she will be instructed to bring back all medication of study period 1 and 2 to a follow-up visit at week 12. The patients who were responders at week 10 and finished the trial at week 12 will be informed about follow-up visit 2 weeks later (week 14).

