Visit week 12 (site visit): the coordinator will review the adverse events, which occurred since the previous visit. A physical exam and blood tests will be performed and the mPDAI will be calculated. The concomitant medications will be assessed. If subject is a woman of child-bearing potential, a reliable and highly effective contraceptive method will be confirmed and they will provide urine samples for pregnancy test at Week 12. A stool sample will be collected from the patient either at visit or days -2 - +2 around the study visit or as mail in. All study medications from period 1 will be collected to assess compliance. All patients who completed visit week 12 and the full treatment period 2 patient will be informed about follow- up visit 2 weeks later (week 14). There will also be a review of glucose diary and hypoglycemic protocol and reporting form.

For all non-responders at week 10, week 12 will be the final follow-up visit in person to collect all study medications from period 1 and 2 to assess compliance.

Week 14 (phone visit): The coordinator will call the patients, who finished the trial at week 12 (responders week 10) and will assess changes in concomitant medication and occurrence of new adverse events since last week.

STUDY VISITS

SCREENING VISIT

Data to be recorded:

- General parameters:
- Initials
- Date of birth
- Sex
- Smoker (yes/no/ex-smoker)
- Race (NIH categories)
- Ethnicity (NIH categories)

Case history

- Date of confirmation of the diagnosis
- Classification of UC before IPAA (proctitis, left sided colitis, pancolitis)
- Type of extraintestinal symptoms
- Specific therapies for pouchitis within the last year
- Type of medication
- Specific therapies for pouchitis within the last 4 weeks
- Type of medication

Examinations

- Vital signs: blood pressure (mm Hg), heart rate (min⁻¹), weight (kg), calculation of BMI, temperature
- Height (cm)
- Physical examination:
- Head (including ENT and eyes)
- Lymphatic system
- Endocrine system
- Lungs and respiratory tract
- Peripheral vascular system
- Cardiovascular system

- Gastrointestinal tract, liver, spleen
- Urogenital system
- Nervous system
- Muscular and skeletal system
- Skin and connective tissue
- Other

each: actual status: Present finding / normal condition / not examined

Blood sampling and measurement of laboratory parameters

- Labs
- Urine pregnancy test (female)
- Stool sample for C. difficile toxin
- Pouchoscopy (standard of care): Evaluation of endoscopic PDAI.

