- Lymphatic system

- Urogenital system

- Endocrine system

- Lungs and respiratory tract

- Peripheral vascular system

- Cardiovascular system

- Nervous system

- Muscular and skeletal system

- Skin and connective tissue

each: actual status: Present finding / normal condition / not examined

Blood sampling and measurement of laboratory parameters

- Labs
- Check if stool sample was received
- In case of early crossover:
 - Urine pregnancy test (female)
 - Dispense stool collection kits for stool samples Period 2

Formal aspects:

- Adverse events (review adverse events diary)
- Confirm reliable and highly effective contraceptive method if subject is a woman of child-bearing potential
- Review of glucose diary and hypoglycemic protocol and reporting form
- Concomitant medication
- Calculation of clinical mPDAI and assess if patient is responder or not (early crossover)
- If patient continues reminder stool Period 1 week 6.
- Early crossover: Dispense study medication for Period 2. Instruct patient to restart study medication on day 6. Instruct to keep study medication from Period 1 and bring back at last visit of Period 2 (week 12) or Period 2 week 10.

VISIT PERIOD 1 WEEK 6: (SITE VISIT; =/- 3 DAYS)

Examinations

- Vital signs: blood pressure (mm Hg), heart rate (min-1), weight (kg), temperature
- Physical examination:
- Head (including ENT and eyes)
- Lymphatic system
- Endocrine system
- Lungs and respiratory tract
- Peripheral vascular system
- Cardiovascular system

- Gastrointestinal tract, liver, spleen
- Urogenital system
- Nervous system
- Muscular and skeletal system
- Skin and connective tissue
- Other
- each: actual status: Present finding / normal condition / not examined

Blood sampling and measurement of laboratory parameters

Labs

- Check if stool sample was received
- Urine pregnancy test (female)

Formal aspects:

- Adverse events (review adverse events diary)
- Confirm reliable and highly effective contraceptive method if subject is a woman of child-bearing potential
- Review of glucose diary and hypoglycemic protocol and reporting form
- Concomitant medication
- Calculation of clinical mPDAI
- Crossover: collect all study medication and dispense study medication for period 2. Instruct patient to restart study medication on day 6.

VISITS PERIOD 2: WEEK 7 AND 8 (PHONE VISIT; +/- 1 DAY)

Blood sampling and measurement of laboratory parameters

- Check if stool sample was received (week 8)

Formal aspects:

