- Adverse events (review adverse events diary)
- Review of glucose diary and hypoglycemic protocol and reporting form
- Concomitant medication
- Calculation of clinical mPDAI
- Remind of stool sample collection at Period 2 week 7 for Period 2 week 8 and at Period 2 week 8 for Period 2 week 10
 - Confirm reliable and highly effective contraceptive method if subject is a woman of child-bearing potential

VISIT PERIOD 2 WEEK 10: (SITE VISIT; =/- 3 DAYS)

- Head (including ENT and eyes)

Examinations

- Vital signs: blood pressure (mm Hg), heart rate (min-1), weight (kg), temperature

- Gastrointestinal tract, liver, spleen

- Physical examination:
- Lymphatic system- Endocrine system- Nervous system
- Lungs and respiratory tract
 Peripheral vascular system
 Skin and connective tissue
- Cardiovascular system Other each: actual status: Present finding / normal condition / not examined

Blood sampling and measurement of laboratory parameters

- Labs
- Urine pregnancy test (female)
- Check if stool sample was received

Formal aspects:

- Adverse events (review adverse events diary)
- Confirm reliable and highly effective contraceptive method if subject is a woman of child-bearing potential
- Review of glucose diary and hypoglycemic protocol and reporting form
- Concomitant medication
- Calculation of clinical mPDAI and assess if patient is responder or not (early termination in case of non-responder). If non-responder, patient should stop medication and will be considered early termination
- If patient continues reminder stool week 12.
- Early termination: Remind patient to come to final visit at Period 2 week 12 and bring all study medication of (if not done already from Period 1 and complete from Period 2). For this patient group at visit Period 2 week 12 only adverse events (review adverse events diary) and concomitant medication will be assessed. An alternative approach is a phone visit Period 2 week 12 and patient returns all study medication 2 before Period 2 week 12.

VISIT PERIOD 2 WEEK 12: (SITE VISIT; =/- 3 DAYS)

Examinations

Vital signs: blood pressure (mm Hg), heart rate (min-1), weight (kg), temperature Physical examination:

- Head (including ENT and eyes)

- Lymphatic system

- Endocrine system

- Lungs and respiratory tract

- Peripheral vascular system

- Cardiovascular system

Cardiovascular system

- Gastrointestinal tract, liver, spleen

- Urogenital system

- Nervous system

- Muscular and skeletal system

- Skin and connective tissue

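### Return of period-1 pens is contradictory for week-6 crossovers, and week-4 early crossovers are told to keep them at home alongside period-2 pens

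*Combined protocol and SAP*

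**What the plan says.** The plan is a single combined protocol and SAP. It describes the return of study drug in several places.

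- **Week-6 crossover, Overview of Trial Sequence (Visit week 6 period 1):** "The patients will be also be instructed to bring back the study medication from study period 1 at the final visit of period 2", which the text identifies as week 12.
- **Week-6 crossover, Study Visits (Visit Period 1 Week 6):** "Crossover: collect all study medication and dispense study medication for period 2".
- **Week-4 early crossover:** the Overview (Visit week 4) dispenses period-2 drug and has period-1 drug brought back at week 12. The Study Visits checklist agrees: "Instruct to keep study medication from Period 1 and bring back at last visit of Period 2" (week 12), with period 2 week 10 as an alternative.
- **Supply given at week 0:** packs "which will be containing treatment until week 6 period 1".
- **Week 10, non-responders:** in the Overview, "he/she will be instructed to bring back all medication of study period 1 and 2 to a follow-up visit at week 12". In the Study Visits checklist, the patient is to "bring all study medication of (if not done already from Period 1 and complete from Period 2").
- **Week 12:** in the Overview, "All study medications from period 1 will be collected to assess compliance". The Study Visits checklist collects drug from both periods.
- **Table Study Visits and Assessments:** the study drug collection row has one mark, at week 12.
- **Measurement of Compliance:** compliance is assessed at the end of each period from pens returned at follow-up visits and at the final visit.

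On labelling, packs carry the patient's unique study ID. For the second period the Overview says "The patient will be given either the placebo or the liraglutide group with his unique study ID for period 2".

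**The concern.** Every patient has one liraglutide period and one placebo period, both supplied as blinded pens. Period-1 and period-2 pens held by the same patient therefore contain opposite treatments. If a patient injects from a period-1 pen during period 2, that dose is the other treatment, which pulls the within-patient contrast towards zero. The trial has 10 patients, and withdrawn patients are not replaced after the first dose, so there is little room to absorb such an error.

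For early crossovers the two sets are at home together by instruction. For week-6 crossovers this depends on which of two incompatible instructions the site follows.

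A lesser point is that pens returned only at week 10 or 12 cannot give a count at the end of period 1, although the compliance section calls for an assessment then.

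**Working it through.** **Which passages conflict**

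| Place | Period-1 pens of a week-6 crossover | Bearing |
|---|---|---|
| Overview, Visit week 6 | brought back at week 12 | late return |
| Study Visits, Week 6 | all collected when period-2 drug is dispensed | return at crossover |
| Visit table, collection row | only mark is week 12 | late return |
| Overview, Visits week 10 and 12; Study Visits, Week 12 | collected at week 12 | either: a final sweep is needed for early crossovers anyway |
| Study Visits, Week 10 | period-1 drug if not already returned | either |
| Measurement of Compliance | end of each period, from pens returned at follow-up and final visits | does not settle it |

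The clash is therefore one narrative sentence against one checklist item, plus a table row without a week-6 mark. For week-4 early crossovers there is no conflict on retention.

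**Supply an early crossover keeps**

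Inputs from the study drug section: 0.6 mg/day in week 1, 1.2 mg/day in week 2, 1.8 mg/day from week 3. The visit window is ±3 days. Milligrams are nominal, because placebo is volume-matched.

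- Six-week regimen: 7×0.6 + 7×1.2 + 28×1.8 = 63.0 mg.
- Used by day 28: 4.2 + 8.4 + 14×1.8 = 37.8 mg. Left: 63.0 − 37.8 = 25.2 mg; 25.2/1.8 = **14 days**.
- Visit on day 25: used 4.2 + 8.4 + 11×1.8 = 32.4 mg. Left: 30.6 mg = **17 days**.
- Visit on day 31: used 4.2 + 8.4 + 17×1.8 = 43.2 mg. Left: 19.8 mg = **11 days**.

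**Effect of whole pens (assumption)**

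A pen holds 6 mg/mL × 3 mL = 18 mg, and 63.0/18 = 3.5, so at least 4 pens are needed. The number dispensed is not stated. With 4 or 5 pens (72 or 90 mg), full dosing up to the visit, no dose reduction and no priming loss:

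| Visit | 4 pens, on the planned day | 5 pens, on the planned day | Range over ±3 days and 4 or 5 pens |
|---|---|---|---|
| Week 4 | 34.2 mg (19 days) | 52.2 mg (29 days) | 28.8–57.6 mg (16–32 days) |
| Week 6 | 9.0 mg (5 days) | 27.0 mg (15 days) | 3.6–32.4 mg (2–18 days) |

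The week-6 row matters only if the late-return instruction is followed.

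**Use during washout**

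With the stated half-life of 11–12 hours and first-order decay, the residual one day after an injection is 0.5^(24/11) to 0.5^(24/12), or 22–25%. The week-10 averaging week starts 21 days after period 2 begins: 504/12 = 42 to 504/11 = 46 half-lives. If the visit is 3 days early, it is 432/12 = 36 to 432/11 = 39. Washout use could at most touch the first weekly average of period 2, and it could carry over active drug only in the liraglutide–placebo sequence.

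**The case against.** The strongest reply has four parts.

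- **The contradiction is narrow.** This stands. The week-10 and week-12 instructions fit a final sweep, and the compliance section allows return at follow-up or final visits. They should not be counted as taking sides.
- **Early-crossover retention is a consistent choice.** This also stands as a reading of the text. Response is decided at the week-4 visit, so a patient cannot know beforehand that pens will be needed there. Changing this is an improvement, not the correction of an error.
- **No harm is shown.** A mix-up requires the patient to use old pens despite new packs and a fixed restart day. Labelling may distinguish the periods, and the phrase about the study ID for period 2 can be read that way. Milligrams left in pens show that a mix-up is possible, not how often it would happen.
- **Return before dispensing could delay crossover.** This is fair. Early crossover exists because of symptom burden, so the fix must not make it conditional on pens being handed in.

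A reader might infer that the trial's estimate is biased, or that carry-over into the primary readout is likely. The documents support neither. No mix-up rate is given, and the half-life arithmetic rules out washout use reaching the week-10 average. A reader might also infer that the efficacy analysis is compromised by late pen counts, but no planned efficacy estimate uses them.

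**Conclusion.** The week-6 instructions contradict each other and must be reconciled; this needs no assumption. For week-4 early crossovers the plan itself places about 14 days of nominal period-1 supply (11–17 days across the window) at home with pens of the opposite blinded treatment. That figure takes the week-0 packs as exactly six weeks of the stated regimen, with dosing up to the visit and no dose reduction. Whole-pen dispensing would raise it.

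The consequence is an avoidable risk of mix-up in a 10-patient crossover. Its effect on the treatment estimate cannot be sized from the documents. Exposure is certain only for week-4 non-responders who take early crossover. For the others it depends on which week-6 instruction is followed. The effect on the compliance check is minor, because late return only delays the period-1 count. The point is worth acting on because the remedy is cheap.

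**What to change.** 1. Reconcile the week-6 narrative, the week-6 checklist and the collection row of the visit table, so that period-1 pens are collected and counted at the week-6 crossover visit, as the checklist already has it.
2. Ask all patients to bring their pens to week 4, and collect and count those of early crossovers at that visit.
3. If an early crossover arrives without pens, do not hold up crossover. Instruct the patient not to use them, and have them returned at the earliest opportunity and not held until week 12.
4. Mark week 4 (early crossover) and week 6 in the collection row, and keep week 12 as the final sweep.
5. Identify packs by period and say how.

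The cost is protocol wording, one table row and a labelling statement. Both visits are already on site. The downside is that every patient must bring pens to week 4 although only some will cross over early.
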